10.3.2 PG calculations

The studies enumerated in the above table report outcomes for Primary Patency for a total number of 966 subjects, whose outcomes are relatively homogeneous (SD = 4.9%; range: 50%-61%) compared to our experience in many other indications where outcomes, even in mature technologies, are typically much more variable. Additionally, the largest studies reported here, encompassing N = 293 and N = 491, were conducted in the US and Netherlands respectively and demonstrated an even narrower range of 50% to 57% respectively.

Taken together, the total N of these studies, coupled with AV fistula creation being a very mature technology demonstrating Primary Patency Rate outcomes that are similar over a wide range of studies in a number of countries over the past 10 years, indicates that the Primary Patency Rate calculated based on these trials is appropriate for use as an PG for our device, which aims to improve upon the relatively homogeneous outcomes reported.

To account for both the variation of subjects between studies and that in percentage of Primary Patency, we applied a statistical model to compute the mean and two-sided 95% confidence interval. The model applied was the generalized linear mixed model (GLMM) with a random effect and a binomial distribution, and the estimation method was maximum likelihood based on the Gauss-Hermite quadrature integral approximation. Study ("paper" in the code below) was included in the model as a random effect. The model was applied using PROC GLIMMIX in SAS® V9.4 using the following SAS® code:

Generalized linear mixed model syntax:

```
proc glimmix data = papers method = quad;
  class paper;
  model success/n = / solution cl dist=binomial;
  estimate 'intercept' intercept 1 / cl ilink;
  random intercept/ subject=paper;
run;
```

Applying this model yielded a mean of 54.7% and a two sided 95% CI of [49.5% to 59.7%]. We therefore specify as our PG for Primary Patency at 6 months, the study's primary endpoint, as 55.0%.

10.4 Sample size justification

Presentation of sample size in this trial is based on the observed Primary Patency rate meeting a PG of 55% (see Section 10.1). Based on limited historical information on the use of VasQ our conservative estimate of device performance is a Primary Patency rate of 70%. A sample of N = 116 evaluable subjects will provide 90% power to demonstrate VasQ meeting the PG. To account for an approximate 10% dropout rate, 129 subjects will participate in this trial. Power computations are based on Exact Binomial computations with a two-sided Alpha = 0.05, designed to demonstrate that the lower

Document title: VasQ FDA pivotal Protocol	Document No. CD0121	Revision 12.0 14 March 2021	Page 36 of 42
--	------------------------	-----------------------------------	------------------

bound of the 95% Exact Binomial confidence interval about observed Primary Patency is above the 55% PG.

In summary, $N = 129$ subjects will be included in this trial to provide 90% power to demonstrate that the VasQ meets its PG.

10.5 Analysis sets

10.5.1 Safety

The safety population will consist of all subjects for whom the study device was implanted.

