7.2 Consent and enrollment

During the screening visits the patients will be introduced to the concept of the study and presented with the informed consent form (ICF). The purpose, procedures, risks, benefits, and alternatives to study participation will be discussed with each potential subject prior to any protocol-dictated procedures. Subjects wishing to participate must give their written informed consent.

The subject must also give Authorization for Use and Release of Health and Research Study Information (HIPAA) in the United States and other written documentation required by local regulations and/or the reviewing IRB prior to any study-related procedures or change in treatment. Patients who consent to participate but do not undergo surgery at all for any reason will be considered as "screen failures" and will not be considered as enrolled. Patients who are excluded intraoperatively due to unusual anatomy (exclusion criteria # 5) for whom VasQ was not implanted, will also be considered as screen failures and will not be considered as enrolled. These patients will not be followed but will be logged and the reason for screen failure will be documented and reported. Only patients which underwent the BCF procedure and had the VasQ implanted will be considered as enrolled in the study. Telephone numbers should be obtained from the patient to ensure the ability to contact them at the required follow-up times. These phone numbers should include all home numbers, work numbers, mobile phone numbers and primary physician numbers. A phone number of a relative or friend should also be requested.

During this visit, a baseline for the concomitant medications of the patients will be determined, as specified in section 11.2.

[REDACTED]

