7.3 Intraoperative procedure

1. Expose the vein and the artery through a 6 cm skin incision.
2. Dissect out the artery and vein. Ensure that there is no stretching or kinking of the vein.
3. Assess whether the target vessels demonstrate any unusual anatomy or vessel dimensions which preclude adequate fit of the VasQ.

[figure not shown]
⁵ National Kidney Foundation, KDOQI Clinical Practice Guidelines For Vascular Access, Update 2006

Document title:
VasQ FDA pivotal Protocol

[figure not shown]
Document No.
CD0121

Revision
12.0
14 March 2021

Page
18 of 42

[figure not shown]
4. Use suture to close off side branches. Do not use metal clips.
5. Use the Laminare Model Selection Tool to gage the vessel external diameter.
6. Attempt to place the "START" notch of the Model Selection Tool over the vessel.
7. VasQ model is chosen based on the gaged vessel diameter. Identify the smallest indentation which can accommodate the vessels, by attempting first to fit the vessel into the smallest indentation marked "START" and then, one by one, attempting the larger indentations until the vessel fits in.
8. The VasQ model is selected according to the model number written next to the smallest indentation that accommodates the vessels. When in doubt, choose the larger model.

Model	Artery diameter D (mm)
4B	$D \leq 3.7$
5B	$3.7 < D \leq 4.2$
6B	$4.2 < D \leq 5.0$
7B	$5.0 < D \leq 5.5$

Model	Vessel Diameter D(mm)
1R	$2.0 \leq D \leq 3.2$
2R	$3.2 < D \leq 3.7$
3R	$3.7 < D \leq 4.1$

9. Thread the VasQ device up the vein by holding the brace, so as to leave the anastomosis suturing area conveniently free and clear.

[figure not shown]
Document title:
VasQ FDA pivotal Protocol

Document No.
CD0121

[figure not shown]
Revision
12.0
14 March 2021

Page
19 of 42

10. Cut the cephalic vein, in preparation for an end-to side anastomosis. Trim the vein at an approximate angle of 50 Degrees.

[figure not shown]
11. Perform an arteriotomy in the artery (5-7mm) and anastomose the cephalic vein to the artery in your routine manner. The area of anastomosis has to be free of fatty tissue.

12. Perfuse the fistula and examine it for adequate flow and lack of leaks.

13. If available, use TTFM⁶ to verify that venous outflow is greater than 200 ml/min.

Slide the **VasQ** along the vein onto the anastomosis.

14. Use a suture to knot two eyelets of the device brace and secure it around the artery.

[figure not shown]
⁶ Transit Time Flow Measurement

Document title:

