8 ADVERSE EVENTS

8.1 Follow-up

Throughout the course of the study adverse events will be followed and recorded as follows:

- All Adverse Events (AEs) will be followed from date of informed consent until the date of the "1 month" visit and recorded in the CRF (excluding events as detailed in section 8.4).
- Assessment of occurrence and severity of the following non-thrombotic access adverse events (per definitions in section 6.4): steal, infection, aneurysm, and seroma will be recorded during each on-site follow-up visit (1, 3, 6, 12, 24 Months visits).
- All other fistula related adverse events will be recorded in each on-site follow-up visit (1, 3, 6, 12, 24 Months visits).
- Serious adverse events (SAEs) will be followed throughout the duration of the study from date of informed consent until date of "24 months" visit or "End of study".

Document title: VasQ FDA pivotal Protocol	Document No. CD0121	Revision 12.0 14 March 2021	Page 27 of 42
--	------------------------	-----------------------------------	------------------

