10.5.2 Full analysis set: Primary Effectiveness Analysis

The full analysis set for the primary effectiveness analysis (FAS_primary) will, consistent with ICH Guideline E9, include all subjects (with brachiocephalic fistulas) for whom the study device was implanted and for whom there is at least one post-procedure Primary Patency measurement.

Handling of missing data: Patients occluded prior to 6 months will be scored as failures even if missing subsequent observations. Patients with missing primary patency at 6 months, but with observed primary patency at later visits (without undergoing interventions) will be considered Success.

Because MI assumes missing at random (MAR), we will conduct sensitivity analyses to assess the sensitivity of our results to alternative assumptions of missingness (see below).

Subjects who died or underwent transplant before 6 months, and were non-occluded at that time of the event, will be excluded from the FAS and reported separately. If such subjects were occluded at or before the time of the event (death or transplant), they will be considered failures and included in FAS for the purpose of the primary analysis.

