10.6 Statistical analysis

10.6.1 Overview

The data will be summarized in tables listing the mean, standard deviation, median, minimum, maximum and number of subjects for continuous data, or in tables listing count and percentage for categorical data where appropriate. Data listing by subject will be provided.

All statistical analyses will be performed and data appendixes will be created using the SAS® system, Version 9.2 or higher. The effects of noncompliance, dropouts, and possible covariates such as age, gender, and center, will be assessed to determine the impact on the general applicability of results from this study.

Safety and subject disposition analyses will be done on the safety analysis set. Primary effectiveness analyses will be done on FAS_primary and PP. Secondary [REDACTED] will be tested on FAS_secondary and PP. Primary and secondary [REDACTED] endpoints will be assessed hierarchically, so that the latter will be tested only if the former’s null was rejected.

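### Subjects with VasQ contact but no final implant fall outside every analysis set, and their follow-up is excluded or unstated, so attempt-related harm and technical failure are missing from the planned rates.

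*Combined protocol and SAP*

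**What the plan says.** - **Enrolment (7.2):** "Only patients which underwent the BCF procedure and had the VasQ implanted will be considered as enrolled in the study". Patients excluded during surgery under exclusion criterion 5, "for whom VasQ was not implanted, will also be considered as screen failures and will not be considered as enrolled". On this group and on patients who have no surgery, 7.2 adds: "These patients will not be followed but will be logged and the reason for screen failure will be documented and reported".
- **Safety set (10.5.1):** "The safety population will consist of all subjects for whom the study device was implanted".
- **FAS_primary (10.5.2):** brachiocephalic subjects "for whom the study device was implanted and for whom there is at least one post-procedure Primary Patency measurement".
- **Sets in use (10.6.1):** "Safety and subject disposition analyses will be done on the safety analysis set".
- **AE window (8.1):** "All Adverse Events (AEs) will be followed from date of informed consent" to the 1-month visit. SAEs are followed from consent to 24 months or end of study, and 8.3 requires all SAEs after consent to be reported to the sponsor.
- **Operation (7.3):** anatomy is assessed at step 3 and the device is sized at steps 5 to 8. Step 9 reads: "Thread the VasQ device up the vein by holding the brace". The vein is cut at step 10, the anastomosis made at step 11 and flow examined at steps 12 and 13. Only then is the device slid into place, secured (step 14) and flow rechecked (step 15).
- **Sensitivity analyses (10.6.7):** these deal with missing 6-month data and do not mention non-implanted subjects.

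**The concern.** Exposure to the device starts at step 9, but a subject counts only once the device is implanted. If an attempt is given up between those points because of misfit, vessel injury or any other reason, the subject has had the device on the vein and still belongs to no analysis set.

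Criterion 5 makes this easier. It covers anatomy or dimensions, seen before or during surgery, that prevent adequate fit of the device, and 7.2 does not confine the intraoperative exclusion to the time before device contact. A misfit found while seating the device could be classed there. Section 9 itself accepts that incorrect placement or sizing can lead to fistula failure.

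At stake are the four main safety rates, the rate of freedom from major device-related adverse events promised in 10.6.5, and the reading of the patency result. All would describe completed implantations only. The disposition tables would not show the gap either, since on an implanted-only set the enrolled and exposed counts coincide by construction.

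**Working it through.** **1. Status of a subject with device contact and no final implant**

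| Item | Source | Status |
|---|---|---|
| Enrolled | 7.2 | No |
| Safety set | 10.5.1 | No; unclear if placed and then removed |
| FAS_primary | 10.5.2 | No; same ambiguity |
| Disposition tables | 10.6.1 | No |
| Worst-case analysis | 10.6.7 | Not mentioned |
| Follow-up | 7.2 | Excluded if criterion 5; otherwise unstated |
| AEs from consent | 8.1 | Yes, on its face |
| SAE report to sponsor | 8.3 | Yes |
| Screen-failure log | 7.2 | Yes if criterion 5; otherwise unstated |

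The follow-up row and the AE row conflict for consented criterion-5 cases.

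**2. The plan's own figure**

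Inputs from 10.4 and 10.6.3: PG 55%, assumed patency 70%, 116 evaluable subjects, exact two-sided 95% interval, success if the lower limit exceeds 55%. With x successes in n, the lower limit is the 2.5% quantile of Beta(x, n − x + 1).

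- The smallest winning count at n = 116 is 75 (64.7%), lower limit 55.2%.
- Power = P(Bin(116, 0.70) ≥ 75) = 91.1%, which agrees with the stated 90%.
- 116/0.9 = 128.9, rounded up to 129.

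The sample size is sound, but for implanted subjects only.

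**3. Attempted non-implants scored as failures**

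The documents give no count, so k = 1 to 5 is an assumption. The denominator becomes 116 + k and the successes stay the same.

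| Implanted result | Lower limit, k = 0 | With added failures | Lower limit |
|---|---|---|---|
| 75/116 | 55.2% | 75/117 (k = 1) | 54.7%, lost |
| 75/116 | 55.2% | 75/121 (k = 5) | 52.7%, lost |
| 81/116 (69.8%) | 60.6% | 81/121 = 66.9% (k = 5) | 57.8%, passes |

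Intermediate results behave in between: 78/116 is lost only with the sixth added failure, and 81/116 only with the eleventh.

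The chance that the sensitivity analysis also clears 55%, at a true 70% in implanted subjects, is P(Bin(116, 0.70) ≥ r), where r is the smallest winning count at 116 + k:

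| k | r of 116 + k | Probability |
|---|---|---|
| 0 | 75 of 116 | 91.1% |
| 1 | 76 of 117 | 87.5% |
| 2 | 76 of 118 | 87.5% |
| 3 | 77 of 119 | 83.0% |
| 4 | 78 of 120 | 77.5% |
| 5 | 78 of 121 | 77.5% |

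**4. A safety rate**

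Use the 129 main-cohort subjects and assume five attempted non-implants, one with a device-related injury. The implanted-only table reads 0/129, upper limit 1 − 0.025^(1/129) = 2.8%. Counting the attempts gives 1/134, upper limit 4.1%. The shift comes from the event that would be left out, not from the denominator: 0/134 gives 2.7%.

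**The case against.** The best case against the point is that the gap is narrow.

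- **Harm would not be invisible.** A reader might infer that it could not surface at all. The documents do not support that: screen failures and their reasons are logged and reported (7.2), and all SAEs after consent go to the sponsor (8.3). This stands. However, a log entry or single SAE report supplies neither a denominator nor a rate, and without follow-up, non-serious or later harm can be missed.
- **The no-follow-up rule is specific.** A reader might take 7.2 to deny follow-up to every abandoned attempt. It does so only for patients with no surgery and for intraoperative criterion-5 exclusions, and the anatomy check and sizing precede device contact. For other abandoned attempts the plan is silent. This also stands, and it is why the status should be written down.
- **Abandonment is not described.** No step in 7.3 says the device is withdrawn, and no consequence is attached to the step 15 recheck. A device placed and then removed could be read as implanted. Poor flow at steps 12 and 13, before seating, is not clearly a device outcome. All fair, but an unclassified subject is a gap in the definition of the analysis sets.
- **A mismatch with the performance goal is not shown.** It is tempting to say that the literature behind the 55% counts every fistula created while this trial counts only completed implants. Section 10.3.1 selected papers reporting patency from AVF placement. Whether those series also left out uncompleted operations cannot be told from the documents.
- **Failure is a worst-case score.** A fistula left without a VasQ may be patent. That is right, and it is a reason to use this scoring in a sensitivity analysis only.

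**Conclusion.** The point holds in this form: subjects with device contact but no final implant are outside the enrolled population, the safety set, FAS_primary and the disposition tables, and their follow-up is either excluded or unstated while 8.1 runs from consent. Attempt-related harm and technical failure are therefore absent from the planned safety and effectiveness rates, apart from the screen-failure log and individual SAE reports.

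The size is unknown, because it depends on a count that the documents do not give. Under the assumed 1 to 5 attempts scored as failures, only results close to the success boundary change. A result near the planning value of 70% does not. The documents therefore do not support inferring that the primary conclusion would be overturned. The prespecified test and its sample size are not in question. This is a gap worth closing because closing it is cheap.

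**What to change.** 1. In 10.5.1, define the safety set as all subjects in whom VasQ placement was attempted, from first device contact (7.3 step 9 onward), and state that devices placed and then removed are included.
2. Report the number of attempts and the technical success rate, and show attempted non-implants in the disposition tables.
3. Reconcile 7.2 with 8.1, and include these subjects' AEs under the existing 8.1 window. Revision 12.0 contains instructions for missed visits during the pandemic, so the study appears to be under way. For subjects already treated, use the screen-failure log and available records, and say that this ascertainment is incomplete.
4. In 10.6.7, add one worst-case analysis of the primary endpoint that counts attempted non-implants as failures.

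Subjects excluded on anatomy before device contact stay screen failures. The primary analysis, the performance goal and the sample size do not change.

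The cost is protocol wording, limited AE follow-up for what is likely to be a few subjects, retrieval of records for past cases, and possibly slightly less favourable rates.

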10.5.2 Full analysis set: Primary Effectiveness Analysis

The full analysis set for the primary effectiveness analysis (FAS_primary) will, consistent with ICH Guideline E9, include all subjects (with brachiocephalic fistulas) for whom the study device was implanted and for whom there is at least one post-procedure Primary Patency measurement.

Handling of missing data: Patients occluded prior to 6 months will be scored as failures even if missing subsequent observations. Patients with missing primary patency at 6 months, but with observed primary patency at later visits (without undergoing interventions) will be considered Success.

Because MI assumes missing at random (MAR), we will conduct sensitivity analyses to assess the sensitivity of our results to alternative assumptions of missingness (see below).

Subjects who died or underwent transplant before 6 months, and were non-occluded at that time of the event, will be excluded from the FAS and reported separately. If such subjects were occluded at or before the time of the event (death or transplant), they will be considered failures and included in FAS for the purpose of the primary analysis.

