STUDY DESIGN	
Structure
 
Main study cohort: Prospective, multi-center, single-arm, open label, enrolling a total of 129 patients referred to surgical creation of new brachiocephalic fistula (BCF). The VasQ will be applied to the AV fistula in all patients. The primary effectiveness endpoint for this trial will be measured at 6 months and compared to a performance goal (PG). Safety will compare descriptively between AE rates for Steal, Infection, Aneurysm and Seroma. Patients will be followed up for an additional 18 months for a total of 2 years. Additionally, this trial has several secondary endpoints.
 
Supplementary study cohort: A total of 15 patients will be prospectively enrolled which are referred to surgical creation of a new forearm arteriovenous fistula. VasQ will be applied to the AV fistula in all patients. Patients will be followed in the same manner as in the Main study cohort, however, the data will be reported separately and also included in the secondary [REDACTED] analysis.
 
Duration
 
Primary endpoint is defined at 6 month post index procedure of fistula placement. Patients will be further followed up to 2 years post index procedure.
 
Visit schedule
 
Screening – per eligibility criteria.
 
Index fistula procedure – VasQ implantation.
 
1, 3 months - Doppler US; Clinical examination, SAE follow up; Dialysis status; Access interventions.
 
6 months – Primary endpoint, Doppler US; Clinical examination, SAE follow up; Dialysis status; Access interventions.
 
9 months – Phone call; SAE follow up; Dialysis status.
 
12 months – Doppler US; clinical examination; X-ray imaging of the arm; SAE follow up; Dialysis status; Access interventions.
 
24 months - Doppler US; clinical examination; X-ray imaging of the arm; SAE follow up; Dialysis status

Document title:
VasQ FDA pivotal Protocol

Document No.
CD0121

Revision
12.0
14 March 2021

Page
6 of 42

ENDPOINTS

Primary effectiveness endpoint:

Primary patency rate at 6 months post AVF creation

1 = Success = Intervention free access patency and flow ≥ 500 ml/min determined by Doppler ultrasound.

0 = Failure = Access occluded or flow < 500 ml/min determined by Doppler ultrasound.

The success rate on this primary endpoint will be compared to a PG of 55.0%.

Secondary [REDACTED] analysis:

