6 ENDPOINTS

6.1 Primary effectiveness endpoint

The primary effectiveness endpoint is primary patency at 6 months post AVF creation. Fistulas are defined as primarily patent¹ if they are free from any intervention up to 180 days (endovascular or surgical) to maintain or restore blood flow and demonstrate minimum flow on Doppler or palpable thrill and audible bruit or are receiving dialysis through the fistula.

- The flow criterion is adapted to a range consistent with a documented² interobserver and intraobserver variability, with various ultrasound systems.
- Due to the COVID-19 pandemic, patients are more prone to miss their on-site doppler examination at 6 months, but still undergo access site assessment (i.e. thrill palpation and bruit evaluations) which is a valid assessment for confirmation of patency (Shenoy et al.). Thus, patients that have bruit and thrill data indicating patency or actively receiving dialysis through the fistula at 6 months without interventions, will be considered as success.

1 = Success = Intervention free access patency at 180 days. Confirmation of fistula patency is established by meeting one of the following three conditions:

1. Artery or vein flow ≥ 500 (-50) ml/min determined by Doppler ultrasound.
or
2. Clinical assessment of palpable Thrill and audible bruit at 6 months
or
3. Patient is receiving dialysis through the fistula at 6 months

Note: if patient is not receiving dialysis through the fistula at 6 months, this will not indicate failure.

0 = Failure = Access underwent intervention before 180 days
or

¹ Shenoy, Surendra, et al. "Clinical trial end points for hemodialysis vascular access: background, rationale, and definitions." Clinical Journal of the American Society of Nephrology 13.3 (2018): 490-494.

² Hoyt Kenneth et al. Accuracy of Volumetric Flow Rate Measurements. An In Vitro Study Using Modern Ultrasound Scanners. J Ultrasound Med 2009; 28:1511–1518

Document title: VasQ FDA pivotal Protocol	Document No. CD0121	Revision 12.0 14 March 2021	Page 14 of 42
--	------------------------	-----------------------------------	------------------

None of the following conditions are met at 180 days:

- Flow \geq 500 (-50) ml/min
- Thrill is palpable and bruit is audible
- Patient is receiving dialysis through the fistula

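### The death/transplant exclusion in section 10.5.2 looks only at occlusion, so subjects who had already failed primary patency by intervention can be removed from the full analysis set

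*Combined protocol and SAP*

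**What the plan says.** Section 6.1 gives two routes to failure at 6 months. One is that none of the patency confirmations is met. The other is the intervention route: "0 = Failure = Access underwent intervention before 180 days". That route does not depend on whether the access was occluded. Section 6.4 agrees: primary patency ends at the first intervention or the first thrombosis, whichever comes first.

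Section 10.5.2 defines FAS_primary and handles early death and transplant separately: "Subjects who died or underwent transplant before 6 months, and were non-occluded at that time of the event, will be excluded from the FAS". These subjects are reported separately. Those occluded at or before the death or transplant stay in as failures. The preceding rule for early failures with later missing data is also written in terms of occlusion. Neither rule mentions a prior intervention.

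Section 10.5.3 builds FAS_secondary on the same criteria. Section 10.6.3 declares success if the lower limit of the two-sided 95% exact binomial interval is above 55.0%.

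**The concern.** The endpoint and the analysis set use different definitions of failure. Under section 6.1 a stenosed but open access treated by angioplasty at month 2 has failed, and nothing later can reverse that. If the subject dies or is transplanted at month 4 with the access open, section 10.5.2 read literally removes that subject. The outcome is not missing. It is known, it is a failure, and it leaves the denominator.

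Removing k known failures changes the rate from x/n to x/(n−k), which can only go up. This is a single-arm trial with one confirmatory rate against a fixed goal, so no control arm shares the distortion. Leaving the conflict in place also means that someone must decide, with the data in hand, which section governs an individual subject.

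**Working it through.** **Inputs from the documents.** Performance goal 55.0% (synopsis and section 10.6.3); assumed device rate 70%, 116 evaluable subjects, 90% power, about 10% dropout and 129 enrolled (section 10.4). On the method, section 10.4 says: "Power computations are based on Exact Binomial computations with a two-sided Alpha = 0.05".

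**Input not in the documents.** The number of subjects with an intervention on a never-occluded access followed by death or transplant before 6 months. Call it m. It is assumed below.

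**Step 1: reproduce the plan's figure.** The exact lower limit L(x, n) is the 2.5% quantile of a Beta(x, n−x+1) distribution.
- L(75, 116) = 55.24% passes and L(74, 116) = 54.35% fails, so 75 successes are needed at n = 116.
- P(X ≥ 75) with X ~ Bin(116, 0.70) is 91.1%. This agrees with the statement "A sample of N = 116 evaluable subjects will provide 90% power to demonstrate VasQ meeting the PG".
- P(X ≥ 75) with X ~ Bin(116, 0.55) is 2.2%, the actual one-tail error.
- 116/0.90 = 128.9, rounded up to 129, matches the enrolment figure.

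**Step 2: shift per excluded failure.** Take 116 as the base with these failures counted.
- Near 55%: 64/116 = 55.2% becomes 64/115 = 55.7%, a rise of 0.5 points.
- Near 70%: 81/116 = 69.8% becomes 81/115 = 70.4%, a rise of 0.6 points.

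**Step 3: can the conclusion change?**

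| m | n analysed | successes needed | same count over 116 |
|---|---|---|---|
| 0 | 116 | 75 (L = 55.24%) | passes |
| 1 | 115 | 75 (L = 55.77%) | passes, no change |
| 2 | 114 | 74 (L = 55.41%) | 74/116, L = 54.35%, fails |
| 3 | 113 | 73 (L = 55.05%) | 73/116, L = 53.47%, fails |

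**Step 4: chance of declaring success at a true rate of 55%.** After m failures are removed, the expected rate among those left is 0.55 × 116/(116−m). The chance of success is P(X ≥ r), with X ~ Bin(116−m, that rate) and r taken from step 3.

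| m (assumed) | rate among those left | chance of success |
|---|---|---|
| 0 | 55.0% | 2.2% |
| 1 | 55.5% | 2.2% |
| 2 | 56.0% | 3.3% |
| 3 | 56.5% | 4.8% |

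The nominal level is 2.5% in this tail. It is exceeded from m = 2.

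**The case against.** Several points on the other side stand.

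- **The gap is narrow.** A thrombosed access that was reopened was occluded before the death or transplant, so section 10.5.2 keeps it as a failure. Only interventions on accesses that never occluded are affected. The term occluded is not defined in the visible text, and part of section 6.4 is redacted, so a clarification there cannot be ruled out.
- **Few subjects are likely.** Exclusion criteria 12 and 13 rule out short life expectancy and a transplant expected within 6 months. If early deaths and transplants fail at the 45% implied by a 55% rate, m = 3 needs at least 3/0.45, or about 7, such events. The whole dropout allowance is 129 − 116 = 13.
- **The worst-case analysis may already cover them.** Section 10.6.7 codes all missing 6-month data as failure and reaches beyond the FAS. It does not name deaths and transplants, so this is arguable rather than settled.

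A reader might infer three stronger conclusions. The documents do not support them.

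- **That the whole exclusion rule biases the rate upward.** The rule also drops event-free subjects while keeping occluded ones as failures, which pushes the rate down. The net direction is not determined.
- **That one subject always decides the result at the boundary.** That depends on the base. If 117 is the correct base, 75/116 passes (55.2%) and 75/117 fails (54.7%). With 116 as the base, one exclusion leaves the required count at 75.
- **That the rescue rule in the same section is a second bias of this kind.** It reads: "Patients with missing primary patency at 6 months, but with observed primary patency at later visits (without undergoing interventions) will be considered Success". Intervention-free patency at a later visit implies patency at day 180. Non-patency found later does not prove failure by day 180. The asymmetry follows from what can be deduced and is not shown to be an error.

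**Conclusion.** The point holds. Sections 6.1 and 10.5.2 conflict, and following section 10.5.2 as written removes already determined failures from FAS_primary and FAS_secondary. For that component the direction is certain: upward, by about 0.5 to 0.6 points per subject. With none or one such subject on a base of 116, the conclusion and the error rate are essentially unaffected. With two, a failing result can pass and the chance of false success rises to 3.3%; with three it is 4.8%. These figures rest on assumed counts and on the literal wording. The plan's sample size is not in question, since it reproduces.

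**What to change.** Reword section 10.5.2 so that a subject who met any section 6.1 failure criterion, intervention or occlusion, before death or transplant stays in the FAS as a failure, and only subjects event-free at that time are excluded. Section 10.5.3 then follows without change. In section 10.6.7, state that the worst-case analysis also counts the excluded event-free deaths and transplants as failures. No rule scoring non-patency first found at a later visit as failure should be added, because it could misclassify fistulas that failed after day 180.

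The cost is a few sentences and a wider worst-case run. No new data are needed, because section 7 already has interventions recorded with their dates. The downside for the sponsor is a slightly less favourable rate if any such subjects occur.
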